## 5. GENERAL METHODOLOGY AND CONVENTIONS

Analysis of safety data through 1 month after Dose 4 (see Section 7.2) may be carried out for all participants when data are available and released. For this reason, the study team will be unblinded after the last participant completes Visit 6 (1 month after Dose 4) and the database snapshot has been taken. The investigator site staff will remain blinded to participant vaccine group until the last participant completes the final visit (Visit 7) and the database has been locked for final analysis.

## 5.1. Hypotheses and Decision Rules

There is no formal hypothesis test and all statistical analyses will be descriptive.

#### 5.2. General Methods

Time points for local reactions and systemic events refer to data within 7 days after each dose.

CIs for all endpoints in the statistical analysis will be presented as 2-sided at the 95% level.

#### 5.2.1. Analyses for Binary Data

Descriptive statistics for categorical variables (eg, proportions) are the percentage (%), the numerator (n) and the denominator (N) used in the percentage calculation, and the 95% CI where applicable.

The exact 95% CI for binary endpoints for each group will be computed using the F distribution (Clopper-Pearson). The 95% CI for the between-group difference for binary endpoints will be calculated using the Miettinen and Nurminen method.

The 3-tier approach will be used to summarize AEs. For both Tier 1 (if any are identified during the study) and Tier 2 events, a 95% CI for the between-group difference in proportions will be calculated based on the Miettinen and Nurminen method. In addition, for Tier 1 events (if any), the asymptotic p-values will also be presented for the difference in proportions, based on the same test statistic and under the assumption that the test statistic is asymptotically normally distributed. For Tier 3 events, counts and percentages for each vaccine group will be provided.

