4.2. Scientific Rationale for Study Design

The Phase 3 study described in this protocol will provide key safety data of 20vPnC in infants to support licensure in this population. Infants born at \geq 34 weeks of gestation and 2 months of age (\geq 42 to \leq 98 days of age) at the time of consent will be eligible if they are naïve to pneumococcal vaccination. This study population has been selected as this is the historical population studied for licensure of 7vPnC and 13vPnC in infants. The participants will be administered either 20vPnC or 13vPnC at 2, 4, 6, and 12 to 15 months of age. This is consistent with the current pneumococcal vaccine recommendations for infants in the United States. 13vPnC will serve as the comparator to 20vPnC for assessment of safety.³¹

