6.3. Measures to Minimize Bias: Randomization and Blinding

6.3.1. Allocation to Investigational Product

Allocation (randomization) of participants to vaccine groups will proceed through the use of an interactive response technology (IRT) system (interactive Web-based response [IWR]). The site personnel (study coordinator or specified designee) will be required to enter or select information including but not limited to the user's identification (ID) and password, the protocol number, and the participant number.

The site personnel will then be provided with a vaccine assignment, randomization number, and dispensable unit (DU) or container number when investigational product is being supplied via the IRT system. The IRT system will provide a confirmation report containing the participant number, randomization number, and DU or container number assigned. The confirmation report must be stored in the site's files.

The study-specific IRT reference manual and IP manual will provide the contact information and further details on the use of the IRT system.

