9.4.1. Safety Analyses

All safety analyses will be performed on the safety population.

Primary	• Descriptive statistics will be provided for each reactogenicity endpoint for each dose and vaccine group. Local reactions and systemic events from Day 1 through Day 7
	 after each dose will be presented by severity cumulatively across severity levels. Descriptive summary statistics will include counts and percentages of participants with the indicated endpoint and the associated Clopper-Pearson 95% confidence intervals (CIs). Between-group differences (20vPnC – 13vPnC) in percentage and 2-sided 95% CIs will be provided. The Miettinen and Nurminen method will be used to derive the 95% CI for the difference in percentages between vaccine groups. AEs will be categorized according to Medical Dictionary for Regulatory Activities (MedDRA) terms. A 3-tier approach will be used to summarize AEs. Under this approach AEs are classified into 1 of 3 tiers: (1) Tier 1 events are prespecified events o clinical importance and are identified in a list in the product's safety review plan; (2) Tier 2 events are those that are not Tier 1 but are considered "relatively common"; a MedDRA preferred term is defined as a Tier 2 event if there are at least 1% of participants in at least 1 vaccine group reporting the event; (3) Tier 3 events are those that are neither Tier 1 nor Tier 2 events. For both Tier 1 and Tier 2 events, the 95% CIs for the difference in percentage of participants reporting the events between the 20vPnC and 13vPnC groups will be calculated using the Miettinen and Nurminen method. In addition, for Tier 1 events, the asymptotic p-values will also be presented for the difference in percentage of participants reporting the events, based on the same test statistic and under the assumption that the test statistic is asymptotially normally distributed. There is no Tier 1 events for each vaccine group. SAEs will be categorized according to MedDRA terms. Counts, percentages, and the associated Clopper-Pearson 95% CIs of SAEs and NDCMCs from Dose 1 to 6 months after Dose 4 will be provided for each vaccine group.
Secondary	• There are no secondary endpoints in the study.

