#### 2.2. Study Design

This Phase 3, multicenter, randomized, double-blind study will be conducted at investigator sites in the United States and potentially other countries to be determined.

Approximately 1500 infants  $\geq$ 42 to  $\leq$ 98 days of age at the time of consent, by their parent(s)/legal guardian(s), will be enrolled. Participants will be randomized in a 2:1 ratio to receive either 20vPnC or 13vPnC (control vaccine) at 2, 4, 6, and 12 to 15 months of age (Doses 1, 2, 3, and 4, respectively) by center-based randomization. Participants will receive the same vaccine (20vPnC or 13vPnC) for all 4 doses.

Participants will be observed for 30 minutes after each vaccination and any reactions occurring during that time will be recorded as AEs. Prompted local reactions (redness, swelling, and pain at the 20vPnC or 13vPnC injection site), systemic events (fever, decreased appetite, drowsiness/increased sleep, and irritability), and use of antipyretic/pain medications occurring within 7 days after each vaccination will be collected via a provided e-diary (or e-diary application). AEs, including nonserious AEs, will be collected from the signing of informed consent through 1 month after Dose 3 and from Dose 4 through 1 month after Dose 4. SAEs and NDCMCs will be collected for the entire duration of the study.

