#### 6.1.1.1.1. Main Analysis

- Estimand: The percentage of participants reporting prompted local reactions (redness, swelling, and pain at the injection site) within 7 days after each dose (Section 2.1).
- Analysis set: Safety population (Section 4).
- Analysis time point: Within 7 days after each dose.
- Analysis methodology: The between-group difference (20vPnC 13vPnC) and the corresponding 2-sided 95% CI will be calculated using the Miettinen and Nurminen method (Section 5.2.1) for each reaction.
- Intercurrent events and missing data: Missing values will not be imputed.

 Reporting results: Count and percentage of participants with the indicated endpoint and the associated 2-sided 95% CI for each and any local reaction after each dose in each vaccine group will be presented by maximum severity across severity levels. Between-group differences (20vPnC – 13vPnC) in these percentages and their 2-sided 95% CIs will also be provided.

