## 6.1.1.2.1. Main Analysis

- Estimand: The percentage of participants reporting prompted systemic events (fever, decreased appetite, irritability, and drowsiness/increased sleep) within 7 days after each dose (Section 2.1).
- Analysis set: Safety population (Section 4).
- Analysis time point: Within 7 days after each dose.
- Analysis methodology: The between-group difference (20vPnC 13vPnC) and the corresponding 2-sided 95% CI will be calculated using the Miettinen and Nurminen method (Section 5.2.1) for each event.

Intercurrent events and missing data: Missing values will not be imputed. CCI •

Reporting results: Count and percentage of participants with the indicated endpoint and the associated 2-sided 95% CI for each and any systemic event after each dose in each vaccine group will be presented by maximum severity across severity levels. Between-group differences (20vPnC – 13vPnC) in these percentages and their 2-sided 95% CIs will also be provided.

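### Should the between-group intervals be stratified by center because randomization is center-based?

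*SAP*

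**What the plan says.** SAP section 2.2 assigns infants 2:1 to 20vPnC or 13vPnC "by center-based randomization". Protocol section 6.3.1 describes the mechanism: "Allocation (randomization) of participants to vaccine groups will proceed through the use of an interactive response technology (IRT) system". Individual infants are therefore allocated, not whole centers. Neither document mentions blocks, a block size or the number of centers.

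For the between-group comparison, SAP section 5.2.1 says "The 95% CI for the between-group difference for binary endpoints will be calculated using the Miettinen and Nurminen" method. The main analysis of local reactions (SAP section 6.1.1.1.1) says the interval "will be calculated using the Miettinen and Nurminen method (Section 5.2.1) for each reaction", and that of systemic events (SAP section 6.1.1.2.1) says it "will be calculated using the Miettinen and Nurminen method (Section 5.2.1) for each event". Protocol section 9.4.1 agrees: "The Miettinen and Nurminen method will be used to derive the 95% CI for the difference in percentages between vaccine groups". None of these visible statements names a stratum. Both SAP analyses report the difference between the percentages shown for each group, by maximum severity.

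On how the intervals are used, SAP section 5.1 says "There is no formal hypothesis test and all statistical analyses will be descriptive".

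**The concern.** When arms are balanced within centers and centers differ in how often parents report reactions, the center differences cancel from the treatment comparison. An unstratified variance still counts them, so the interval comes out wider than its 95% label implies. The usual advice is to reflect in the analysis any factor used in the randomization.

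The comparison is not incidental. Protocol section 4.2 says "13vPnC will serve as the comparator to 20vPnC for assessment of safety", and these intervals are the planned between-group summary of reactogenicity after each of four doses. An over-wide interval would include zero somewhat too often, which in a safety comparison could make a real excess look less distinct. A reader also cannot tell from the text whether center was left out deliberately.

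**Working it through.** **1. The plan's own precision figure.** Protocol Table 4 gives the chance of seeing at least one AE, 1 - (1 - p)^n. At n = 1000 and p = 0.003 this is 95.04%, against 95.0% printed; all ten cells reproduce. The sample size rests on this, not on the width of a between-group interval.

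**2. Direction.** Let rho be the share of the variance p(1 - p) that lies between centers. With arms balanced within center:

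- variance used by the unstratified interval: p(1 - p)(1/n1 + 1/n2)
- actual variance of the difference: (1 - rho) times that
- ratio of half-widths: sqrt(1 - rho); coverage: 2*Phi(1.96/sqrt(1 - rho)) - 1

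The interval is thus too wide, never too narrow. At p = 20%, n1 = 1000 and n2 = 500, the half-width is 1.96 * sqrt(0.2 * 0.8 * 0.003) = 4.29 points. Accounting for center would give 4.19 (rho 0.05), 4.07 (rho 0.10) or 3.84 (rho 0.20). Formula coverage is 95.6%, 96.1% and 97.2%.

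Simulation of the unstratified interval (25, 50 or 100 centers, rates 5-50%, blocks of 3 or 6, beta-distributed center rates) gave 94.8-95.4% at rho 0.01, 95.3-95.8% at 0.05, 95.8-96.1% at 0.10 and 96.6-97.2% at 0.20. With simple allocation, coverage was 94.6-95.3% at every rho.

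**3. Size under realistic conditions.** The documents give no center count, block size, event rate or center spread, so all are assumed: 50 or 100 centers of unequal size, blocks of 3 or 6 with incomplete last blocks, 10% of diaries missing, centers under 12 infants pooled, rates of 20% and 50%, and no vaccine effect. There were 5000 trials per setting (150 for half-widths). The Monte Carlo error of a coverage figure is sqrt(0.95 * 0.05/5000) = 0.003. Stratification is Miettinen-Nurminen with Mantel-Haenszel weights.

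| Center logit SD | Stratified/unstratified half-width, blocked | Unstratified coverage, blocked | Half-width ratio, unblocked |
|---|---|---|---|
| 0.2 | 0.997-1.000 | 0.945-0.955 | 1.009-1.011 |
| 0.4 | 0.985-0.994 | 0.949-0.958 | 0.997-1.004 |
| 0.8 | 0.944-0.972 | 0.953-0.964 | 0.957-0.981 |

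Stratified coverage with blocking was 0.947-0.955 throughout. Unstratified coverage without blocking was 0.949-0.958, so the blocked result at SD 0.4 cannot be told apart from it. To link the two scales, rho is roughly p(1 - p) * SD^2 for small SD: at p = 50%, 0.25 * 0.04 = 0.01 (SD 0.2) and 0.25 * 0.16 = 0.04 (SD 0.4).

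At a 50% rate the half-width of 5.64 points becomes 5.63 (SD 0.2), 5.56-5.58 (SD 0.4) or 5.32-5.39 (SD 0.8). With 25% of diaries missing, the changes are 0 to +0.3%, -0.3 to -1.3% and -2.4 to -5.4%. At a 3% rate with blocking and no pooling, stratifying gains nothing at SD 0.2-0.4 (0 to +1.2%).

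**4. What stratifying would cost.** With blocking, the two estimates have almost the same sampling SD (ratio 0.988-1.004), so stratifying mainly relabels the width. The stratified difference departs from simple subtraction of the displayed percentages by 0.11-0.30 points on average (0.20-0.50 with 25% missing). The largest saving at SD 0.2-0.4 is 1.5% of 5.64 = 0.085, about 0.09 points. Over that range the mismatch is larger than the gain.

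**The case for a change.** The best case for a change is that the direction is certain once blocking is granted, that center is already recorded, and that one sentence would tell the reader whether the omission is deliberate. At SD 0.8 the effect is visible: half-widths 2.8-5.6% too long and coverage up to 0.964. With still larger center differences (rho 0.30), simulated coverage reached 97.2-98.1%, so the excess is not slight under every conceivable spread. Even without blocking, one set of runs at SD 0.8 and a 50% rate found the stratified estimate about 3-4% more precise (SD ratio 0.964-0.969).

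All of that stands as arithmetic. It does not carry the recommendation. Blocking is not stated, and nothing in the documents points to center differences as large as SD 0.8. Without blocking, stratifying at SD 0.2-0.4 can lengthen the interval by up to 1.1% with pooling or 3.6% without. A stratified primary interval would need a small-center pooling rule and a footnote explaining why the differences do not match the displayed percentages. Limiting it to common events would also put two methods in one severity table. Sponsor redactions in SAP section 6.1 mean that a supportive analysis by center cannot be ruled out.

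**Conclusion.** No change follows. The planned interval is valid. It is nominal if allocation is not blocked within center, and if it is blocked, negligibly to mildly conservative: 0 to 1.5% too wide at logit SD 0.2-0.4 and about 3 to 6% at SD 0.8. These sizes rest on assumed center numbers, block sizes, rates and spreads, and on individual allocation within center, which is how protocol section 6.3.1 reads. Cluster allocation would reverse the direction, but nothing describes it.

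The consequences are small. The primary estimands are percentages in each group (protocol section 3, SAP section 2.1), and their Clopper-Pearson intervals are unaffected. No hypothesis, margin or stated figure depends on the width of the difference. An analyst who finds no stratum named will run the ordinary unstratified method, which is a sensible reading and matches the percentages on the page. Choosing one uniform, transparent interval over a marginally shorter stratified one is a fair trade-off in a descriptive safety study. A sentence saying that center was left out by intent would be harmless, but the analysis does not need it.

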#### 5.2.2. Analyses for Continuous Data

Unless otherwise stated, descriptive statistics for continuous variables are n, mean, median, standard deviation, minimum, and maximum.

#### 5.3. Methods to Manage Missing Data

A partial AE start date (missing day, missing both month and day) will be imputed by assigning the earliest possible start date using all available information, such as the stop date of the AE and the vaccination date(s) from the same participant, following the Pfizer standard of handling incomplete AE start date. An AE with a completely missing start date is not allowed in the data collection.

No additional imputation will be applied to other missing data.

## 6. ANALYSES AND SUMMARIES

#### **6.1. Primary Endpoints**

## 6.1.1. Primary Safety Endpoints

## 6.1.1.1. Local Reactions

Results from local reactions after each dose (Dose 1, Dose 2, Dose 3, and Dose 4) will be summarized separately.

#### 6.1.1.1.1. Main Analysis

- Estimand: The percentage of participants reporting prompted local reactions (redness, swelling, and pain at the injection site) within 7 days after each dose (Section 2.1).
- Analysis set: Safety population (Section 4).
- Analysis time point: Within 7 days after each dose.
- Analysis methodology: The between-group difference (20vPnC 13vPnC) and the corresponding 2-sided 95% CI will be calculated using the Miettinen and Nurminen method (Section 5.2.1) for each reaction.
- Intercurrent events and missing data: Missing values will not be imputed.

 Reporting results: Count and percentage of participants with the indicated endpoint and the associated 2-sided 95% CI for each and any local reaction after each dose in each vaccine group will be presented by maximum severity across severity levels. Between-group differences (20vPnC – 13vPnC) in these percentages and their 2-sided 95% CIs will also be provided.

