maximum severity grade = highest grade (maximum severity) within 7 days after vaccination (Day 1 through Day 7) among severity grades reported for that local reaction in the e-diary.

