#### 3.1.1.2. Systemic Events (Systemic Event Symptoms and Fever)

The systemic events assessed and recorded in the e-diary are fever, decreased appetite, drowsiness/increased sleep, and irritability from Day 1 through Day 7, where Day 1 is the day of each dose.

Maximum temperature range over the period from Day 1 through Day 7 will be mapped into the ranges described in Table 6 for summary of maximum temperature.

The systemic events of decreased appetite, irritability, and drowsiness/increased sleep will be assessed by participants' parents/legal guardians as mild, moderate, or severe according to the grading scale in Table 5. Grade 4 will not be collected in the e-diary but will be collected as an AE on the CRF.

Systemic Event	Mild	Moderate	Severe	
	Grade 1	Grade 2	Grade 3	Grade 4 a
Decreased appetite	Decreased interest	Decreased oral	Refusal to feed	Emergency room visit or
(loss of appetite)	in eating	intake		hospitalization for severe
				decreased appetite (loss of
				appetite)
Drowsiness	Increased or	Slightly subdued,	Disabling, not	Emergency room visit or
(increased sleep)	prolonged	interfering with	interested in usual	hospitalization for severe
	sleeping bouts	daily activity	daily activity	drowsiness (increased sleep)

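### The protocol presents prompted-event severity cumulatively; the SAP presents it by maximum severity with between-group CIs on those rows, so mild and moderate rows can be misread and no moderate-or-worse contrast is specified

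*SAP*

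**What the plan says.** Protocol 9.4.1 (Safety Analyses) states that local reactions and systemic events from Day 1 through Day 7 "after each dose will be presented by severity cumulatively across severity levels". It asks for counts, percentages, Clopper-Pearson CIs, and between-group differences with Miettinen-Nurminen CIs.

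SAP 6.1.1.1.1 states that the count, percentage and CI "for each and any local reaction after each dose in each vaccine group will be presented by maximum severity across severity levels", and then that the between-group differences "in these percentages and their 2-sided 95% CIs will also be provided". SAP 6.1.1.2.1 uses the same construction for systemic events: "for each and any systemic event after each dose in each vaccine group will be presented by maximum severity across severity levels". The word cumulatively appears in neither SAP section.

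The SAP derives one grade per infant, reaction and dose: "maximum severity grade = highest grade (maximum severity) within 7 days after vaccination". For fever, "Maximum temperature range over the period from Day 1 through Day 7 will be mapped into the ranges described in Table 6". Those four ranges do not overlap, and they are the same as in Table 3 of the protocol (8.2.2.2.2).

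SAP Section 2 lets the SAP modify the protocol, with major changes to a primary endpoint definition or its analysis also going into a protocol amendment. The SAP version history lists version 1 only, with no changes or rationale. Protocol Amendment 1 is described as concerning the timing and format of Visits 5 to 7.

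**The concern.** The trial's purpose is to describe safety, and it has no hypothesis test. The between-group intervals are therefore its only comparative output on the prompted events, and each row that carries one should have a clear direction.

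A cumulative row has one: a higher percentage at a given grade or worse is less favourable. A mutually exclusive mild or moderate row does not. An infant leaves the mild row by having no reaction or by having a worse one, and the difference cannot tell these apart. Its 95% CI can exclude 0 in the apparently favourable direction when tolerability has become worse.

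There are six graded prompted events (three local, three systemic) and four doses. With two lower grades each, 6 x 4 x 2 = 48 mild and moderate rows would carry such an interval. How often the effect would occur among them cannot be derived from the documents.

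**Working it through.** **Inputs.** Group sizes are 1000 and 500 (protocol 4.1.2). CIs are 2-sided at 95% (SAP 5.2) by Miettinen-Nurminen (SAP 5.2.1). Neither document gives reaction rates by grade, so all rates below are assumptions.

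**The plan's own figure.** Nothing in the plan quantifies the precision of a reactogenicity difference. The only computed design figure is protocol Table 4, the chance of at least one AE, 1-(1-p)^n. For n = 1000 and p = 0.3% this is 1 - 0.997^1000 = 95.04%, against 95.0% stated. All ten entries reproduce, and this point does not affect them.

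**How the rows relate.** Let D be the 20vPnC minus 13vPnC difference in percentage. With one maximum grade per infant:

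- D(mild) = D(any) - D(moderate or worse)
- D(moderate) = D(moderate or worse) - D(severe)

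The mild difference is therefore negative whenever moderate-or-worse reactions rise by more than reactions overall.

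**Interval.** The limits are the values d that solve (D - d)^2 / V(d) = 1.96^2, where V(d) = [p1(1-p1)/n1 + p2(1-p2)/n2] x N/(N-1), with p1 and p2 the maximum-likelihood estimates restricted to p1 - p2 = d, and N = n1 + n2.

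**Illustration A: a 5-point shift from mild to severe.**

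| Row | 20vPnC | 13vPnC | Difference, points (95% CI) |
|---|---|---|---|
| Mild only | 250/1000 | 150/500 | -5.0 (-9.9 to -0.2) |
| Moderate only | 180/1000 | 90/500 | 0.0 (-4.3 to 4.0) |
| Severe (both displays) | 70/1000 | 10/500 | +5.0 (2.9 to 7.0) |
| Moderate or worse | 250/1000 | 100/500 | +5.0 (0.5 to 9.3) |
| Any severity | 500/1000 | 250/500 | 0.0 (-5.4 to 5.4) |

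The identities check: 0.0 - 5.0 = -5.0 for mild, and 5.0 - 5.0 = 0.0 for moderate.

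**Illustration B: a 6-point shift from mild to moderate.** The rates are 14/15/1% on 20vPnC and 20/9/1% on 13vPnC.

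- Exclusive rows: mild -6.0 (-10.2 to -2.0), moderate +6.0 (2.5 to 9.3), severe 0.0 (-1.4 to 1.0).
- Cumulative rows: any 0.0 (-5.0 to 4.8), moderate or worse +6.0 (2.4 to 9.4), severe 0.0 (-1.4 to 1.0).

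With 15% assumed attrition (850 vs 425), the mild row is -6.0 (-10.6 to -1.7).

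**How large a shift is needed.** With the any-severity rate held equal, the upper limit of the mild row first falls below 0 at these observed shifts:

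| 13vPnC mild rate | Shift, points |
|---|---|
| 5% | about 2.2 |
| 10% | about 3.0 |
| 20% | about 4.2 |
| 30% | about 4.8 |

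From a 20% mild rate, the chance that the mild-row CI excludes 0 is about 30%, 68% and 84% for true shifts of 3, 5 and 6 points.

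**When it does not appear.** In illustration A, a 4.5-point shift (255/1000 vs 150/500) gives a mild row of -4.5 (-9.4 to 0.3). If reactions also rise overall (16/16/1% vs 20/9/1%), the mild row is -4.0 (-8.3 to 0.1).

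**The case against.** The SAP never says that its rows are mutually exclusive. A moderate-or-worse row is also computed from the maximum grade, so deriving that grade does not settle the matter. The protocol does not define cumulatively. Parts of the SAP near the reactogenicity definitions are redacted and could contain row definitions. This stands: exclusive rows are the natural reading, not an explicit statement.

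A reader might infer that the SAP would conceal a rise in severe reactions. The documents do not support that. Severe is the top diary grade, so its row is identical under both displays; in illustration A it shows +5.0 (2.9 to 7.0) in the same table as the mild row. In illustration B the moderate row shows the rise.

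A reader might also infer that no overall contrast is planned. But the estimand is the percentage reporting the reaction, and the methodology bullet says the difference and CI "will be calculated using the Miettinen and Nurminen method (Section 5.2.1) for each reaction". That leaves room for an any-severity row, which is the same under both displays.

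It is tempting to call a mild-row result a significant benefit. Protocol 9.1.1 and SAP 5.1 exclude formal testing, so the most that can be said is that a descriptive 95% CI excludes 0. No decision rule depends on it.

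Nor does the SAP depart from the protocol's fever ranges: its Table 6 repeats protocol Table 3. The tension is inside the protocol, between the ranges in 8.2.2.2.2 and the cumulative presentation in 9.4.1.

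Finally, the SAP may modify the protocol, and a change of display may not count as major. That is fair, but no change is recorded, so a reader cannot tell whether it was intended.

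**Conclusion.** The point holds as an unrecorded difference between protocol and SAP on the display of the primary reactogenicity endpoints. On the natural reading of the SAP, the mild and moderate rows carry differences whose sign does not indicate better or worse tolerability. The moderate-or-worse contrast implied by a cumulative display is not specified.

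Under assumed rates with equal any-severity percentages, an observed shift of roughly 2 to 5 points out of the mild row, for 13vPnC mild rates of 5% to 30%, is enough to put that row's CI wholly below 0. Smaller shifts, or a rise in total reactions, can remove the effect.

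This is a risk of misreading and a missing contrast. It is not a numerical error, a hidden safety signal or a false test result. It rests on three assumptions: that the rows are exclusive, that cumulative means at this grade or worse, and the illustrative rates.

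**What to change.** In SAP 6.1.1.1.1 and 6.1.1.2.1, state that percentages, between-group differences and 95% CIs are given for cumulative categories: any severity, moderate or worse, and severe. Show the maximum-severity distribution as counts and percentages without differences. If exclusive rows with differences are intended, record this as a departure from protocol 9.4.1 and give the reason.

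For fever, keep the ranges shared by protocol Table 3 and SAP Table 6, and add differences with CIs for at or above 38.0°C, above 38.4°C, above 38.9°C and above 40.0°C. This reconciles protocol 8.2.2.2.2 with 9.4.1.

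The cost is SAP wording and table shells. The data, population and interval method do not change.
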